9.5 Data Safety Monitoring Board (DSMB) / Safety Committee

The assessment of a Data Safety Monitoring Board has been taken into consideration by the involved investigators of this study. There has been chosen not to establish a DSMB for the following reasons:

- The interventional product used in this study is not a medicinal product.
- The nutritional intervention will be given under strict supervision of a dietician
- Subjects included in this study are otherwise healthy, mentally capable, non-critically-ill subjects and are not incapacitated.
- The interventional diet used in this study is not known to harm the involved subjects.

10. STATISTICAL ANALYSIS

Categorical data will be presented as numbers (percentage) and continuous variables as mean (standard deviation/normal distribution) or median (interquartile range/no normal distribution).

An Intention-to-treat analysis will be conducted to account for the feasibility of the caloric restricted and ketogenic diet. A two-sided significance level of 0.05 will be used for all primary and secondary analyses unless stated otherwise.

Statistics will be computed using IBM SPSS software version 21.0 (Chicago, IL) or R version 4.0.2 or newer.

10.1 Primary study parameter

The primary endpoint is the reduction in size (in cm) of the largest diameter of the largest hepatocellular adenoma after 6 months, compared to our matched historical controls. A multivariable linear regression model will be used to estimate the difference in tumour regression between the treatment group and the historical control group. The model will be adjusted for age, change in body weight, the ketogenic diet and oral contraceptive use at baseline.

Subpopulation: the same model will be constructed but will not be adjusted for oral contraceptive use at baseline.

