4.4 Sample size calculation

We based our sample size calculations on the large multicentre retrospective cohort mentioned earlier study (30). This study calculated a median (IQR) HCA diameter at baseline of 82.0mm (65-100) and at 6-month follow-up of 65.0mm (56-80).

Based on this, considering a relevant effect of 20% difference in mean tumour size after 6 months, we estimated an average additional decrease of 13mm in the intervention group when compared to our earlier collected (30).

With a two-sided alpha set at 0.05, power at 0.95, we calculated that at least 51 subjects are required. Anticipating +/- 10% drop-out, we aim to include 55 participants in this study. We aim to include all study subjects in 1 – 1,5 years.

Since the subpopulation is a pilot study, we did not perform a sample size calculation. For this subpopulation, we hypothesized a sample size of 20 subjects. We estimated that this sample size is large enough to provide a reliable initial answer.

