8.1.3 Other study parameters

- Baseline subject characteristics such as age, sex, weight, length, BMI, oral contraceptive use, other medication use, comorbidities, size of hepatocellular adenoma at baseline, multiple or single lesion, amount of hepatocellular adenoma's at baseline, subtype of hepatocellular adenoma, time since initial diagnosis, time since last imaging study, imaging study provided (MRI/CT/Ultrasound), referring hospital and active pregnancy wish.
- Macronutrient intake (3-day food diary)
- Physical activity by IPAQ questionnaire (70, 71), Dutch version 1, 23-01-2011. Higher score means a higher level of physical activity
- Incidence of symptomatic HCA, defined as:
 - o HCA rupture/bleeding confirmed on CT / MRI
 - o for which admittance into the hospital or (endovascular) treatment is indicated.

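### The primary regression of absolute shrinkage omits baseline adenoma diameter, so size imbalance left after matching goes uncorrected and the model's residual variance is roughly doubled

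*Protocol*

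**What the plan says.** **Outcome and model (section 10.1).** The outcome is a raw change score: "The primary endpoint is the reduction in size (in cm) of the largest diameter of the largest hepatocellular adenoma after 6 months". The model is named: "A multivariable linear regression model will be used to estimate the difference in tumour regression between the treatment group and the historical control group". Its covariates are listed: "The model will be adjusted for age, change in body weight, the ketogenic diet and oral contraceptive use at baseline". Section 10.2 reuses the same model and list to look for predictors of the primary endpoint. The subpopulation model is the same without the contraceptive term.

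**Where baseline size does appear.**
- Section 3 makes adenoma size one of seven matching variables. They are combined into one propensity score, with 1:1 optimal nearest-neighbour matching without replacement. Covariate balance is then examined to judge whether matching succeeded; no threshold and no consequence is given.
- Section 3 also lists diameter at diagnosis among the predictors in the published regression model that supplies the controls.
- Section 8.1.3 records it for each participant: "size of hepatocellular adenoma at baseline, multiple or single lesion".

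**Figures (section 4.4).** The historical cohort had a "median (IQR) HCA diameter at baseline of 82.0mm (65-100) and at 6-month follow-up of 65.0mm (56-80" mm). The target is given as "we estimated an average additional decrease of 13mm in the intervention group". On numbers: "With a two-sided alpha set at 0.05, power at 0.95, we calculated that at least 51 subjects are required", and "Anticipating +/- 10% drop-out, we aim to include 55 participants in this study".

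**The concern.** The cohort's IQR narrows from 35 mm to 24 mm over six months. For the spread to narrow like this, large lesions must on average lose more millimetres than small ones, so the change score depends on where a lesion started. Two consequences follow if the starting size is not in the model.

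- **Bias.** Any difference in mean baseline size that survives matching passes into the estimated diet effect. It can go either way: larger lesions in the diet group would flatter the diet, and smaller ones would hide an effect.
- **Precision.** Variation that baseline size would explain stays in the error term and widens the reported confidence interval.

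This is not detail that the protocol leaves for later. It names a specific model and covariate list, and that list is the problem. The comparison is non-randomised and open-label, so adding the covariate after outcomes are known would carry less weight than fixing it now.

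**Working it through.** **Inputs.** From section 4.4: baseline IQR 65–100 mm, follow-up IQR 56–80 mm, target 13 mm, two-sided alpha 0.05, power 0.95, 51 subjects. Assumptions: SD = IQR/1.349 (near-normality), the same SDs and correlation in both groups, and 51 read as the number analysed per group under 1:1 matching. The correlation r between baseline and six-month diameter is not in the documents, so a range is shown.

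s0 = 35/1.349 = 25.9 mm; s1 = 24/1.349 = 17.8 mm.

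**1. The plan's own figure.** Section 4.4 states no SD. With n = 2(1.960 + 1.645)² SD²/13², an SD of 17.8 mm gives 48.7, so 49 per group (50 by the t distribution). An SD of 18 mm gives 50 (51 by t). The stated 51 is therefore reproduced to within 2 using the spread of follow-up diameters. The baseline SD gives 104 per group and does not reproduce it.

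**2. Residual variance without and with baseline diameter.**
- Without: V_change = s0² + s1² − 2r·s0·s1
- With: V_adj = s1²(1 − r²)
- Ratio, with k = s0/s1: 1 + (k − r)²/(1 − r²). The minimum is k², at r = 1/k.

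Here k = 35/24 (the 1.349 cancels), so the minimum is (35/24)² = 2.13, at r = 0.69. Baseline diameter thus accounts for at least 1 − 1/2.13 = 53% of the change-score variance.

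| r | SD without (mm) | SD with (mm) | Variance ratio | Power without | Power with | n per group for 95%, without / with |
|---|---|---|---|---|---|---|
| 0.5 | 23.0 | 15.4 | 2.22 | 82% | 99% | 82 / 37 |
| 0.7 | 18.5 | 12.7 | 2.13 | 94% | >99% | 53 / 25 |
| 0.8 | 15.8 | 10.7 | 2.20 | 98% | >99% | 39 / 18 |

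Power is for 13 mm with 51 per group. Without the covariate, the planned 95% needs r of about 0.71 or more.

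**3. Sensitivity of the factor.** A log-normal reading of the quartiles gives SDs of 28.3 and 18.1 mm and a floor of 2.44. If the listed covariates explained a share q of baseline variance and none of follow-up, the floor would be 2.13(1 − q): 2.0 at q = 0.06 and 1.7 at q = 0.2.

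**4. Effect of matching on size.** An illustrative simulation drew 51 treated and 180 controls, with baseline size and six other covariates in an estimated propensity score and 1:1 optimal matching. Mean size was the same in both source populations.

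| r | Model-reported variance ratio | True sampling variance ratio | True / reported variance, unadjusted model |
|---|---|---|---|
| 0.5 | 2.26 | 1.37 | 0.59 |
| 0.7 | 2.12 | 1.35 | 0.61 |
| 0.85 | 2.34 | 1.47 | 0.67 |

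Mean absolute size imbalance after matching was 0.09 SD. The unadjusted model's standard error was too large by √(1/0.67) = 1.22 to √(1/0.59) = 1.30.

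The power figures in step 2 make no allowance for this. Making one at r = 0.5: the expected z is 13/(23.0·√(2/51)) = 2.86, and Φ((2.86 − 1.96)/√0.59) is about 88%, not 82%. At r = 0.7 the same step gives about 98%.

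**5. Shift from leftover imbalance.** The slope of shrinkage on baseline is 1 − r·s1/s0: 0.66, 0.53, 0.45 and 0.38 at r = 0.5, 0.69, 0.8 and 0.9.
- 0.1 SD = 2.6 mm: shift of 1.7 mm (r = 0.5) to 1.0 mm (r = 0.9)
- 0.25 SD = 6.5 mm: shift of 4.3 mm (r = 0.5) to 2.5 mm (r = 0.9)

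**The case against.** The best defence is that size is handled in the design: it is a matching variable, and balance will be checked. Much of this stands. In the simulation, matching left only 0.09 SD of imbalance on average (about 2.3 mm) and removed part of the variance. What does not follow is that the stated model is adequate. A single score built from seven variables does not make diameters equal within pairs, the balance check has no stated consequence, and the regression neither adjusts for size nor mentions the pairs. It therefore cannot recover the precision that matching provides. The simulation is also favourable, because it assumed equal mean size in both sources. Section 4.1 admits adenomas of any size, while the control cohort's lower quartile is 65 mm.

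A second defence is that power may be sufficient anyway. At r = 0.8 it is, and once matching is allowed for it may be at r = 0.7 too. The loss is clear only at lower correlations.

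Several stronger readings are tempting, but the documents do not support them:
- **The variance of the effect estimate doubles.** Only the residual and model-reported variance does; true sampling variance rises less because size is matched.
- **Diameter is the strongest determinant of shrinkage.** The protocol ranks nothing, and its prediction model concerns regression below 5 cm, not millimetres lost. The 53% share shows that diameter matters; no competing factor is quantified.
- **A 10 mm imbalance is to be expected.** That is 10/25.9 = 0.39 SD, which is large after matching on size.
- **Adjustment makes the result safe whatever the overlap.** If few controls resemble the smaller new lesions, a regression term extrapolates.

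**Conclusion.** The point holds in limited form. The stated primary model leaves out a covariate that the protocol collects, matches on and names as a predictor of regression. Residual, model-based variance is inflated by a factor of at least 2.13 at any r, if the IQR-based SDs apply to the matched groups and the listed covariates explain little of baseline size. True sampling variance rises by about 1.35 to 1.47-fold in one illustrative simulation. The practical costs are an overstated standard error, power below plan if r is low, and an uncorrected shift of about 1 to 4 mm, or 8% to 33% of the 13 mm target, if 0.1 to 0.25 SD of imbalance remains. The correlation is unknown, so the power loss cannot be fixed at one figure. The plan should be changed, but the omission does not by itself invalidate the comparison.

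**What to change.** In section 10.1, add baseline diameter of the largest adenoma as a prespecified covariate in the primary model. Modelling six-month diameter adjusted for baseline diameter is equivalent and gives the same estimate of the diet effect. Carry the change into section 10.2, which reuses the model. In the subpopulation use the same single linear term and nothing more elaborate: with about 20 subjects and 20 controls there is little room for extra parameters, and those women are selected for little or no earlier shrinkage, so the cohort's narrowing spread does not describe them. Subtype and number of lesions need not become mandatory covariates; no figure in the protocol supports requiring them.

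The cost is one sentence and one degree of freedom per model. Baseline size is already recorded for participants and must be available for the controls, because they are matched on it. The change should be made before outcomes are examined.

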3. STUDY DESIGN

We aim to answer our research questions by conducting a single-centre, proof of concept interventional matched cohort study.

Main study population

Our newly acquired cohort will be compared with a matched historical control group acquired during an earlier study (30). This large multicentre retrospective cohort developed a prediction model for patients with HCA (N=180, HCA diameter at baseline: 82.0mm (65-100) and follow-up: 65.0mm (56-80) (Median (IQR)). This prediction model estimates the probability of HCA regression to <5cm at 1 and 2 years follow-up (30) with an internally validated c-index of 0.79.

The prediction model the authors developed was translated into a chance assessment tool. Included predictors in this model are: diameter at diagnosis, diameter at first follow-up, dates of diagnosis and first follow-up and HCA-subtype. This chance assessment tool will provide the estimated chance of regression to 0,5 cm at 1-2 years after diagnosis and is currently used in clinical practice at Erasmus University Medical Center. The chance tool is available via <https://hcaprediction.shinyapps.io/calculator/>. This prediction model will also be used for our included patients, as part of standard of care.

Matching to the earlier acquired patient cohort will be based on subject age, use of oral contraceptives, ethnicity, weight, type of HCA, size of HCA and number of lesions at baseline. Matching will be conducted via optimal nearest-neighbor matching on propensity score, in a 1:1 ratio without replacement (63). Examination of the balance on covariates resulting from the matching method will be conducted to determine if matching has been successful.

Study subpopulation

As a nested pilot-study we aim to acquire a small sub-cohort of subjects with a slightly different population base criterium, see chapter 4.1. The inclusion and exclusion criteria will be applied in the same way as in the main study population.

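### The primary regression leaves out five of the seven matching variables, including baseline adenoma size and type, so precision is probably lost and the test is probably conservative

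*Protocol*

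**What the plan says.** Section 3 pairs each diet patient with one patient from a historical cohort of 180: "Matching will be conducted via optimal nearest-neighbor matching on propensity score, in a 1:1 ratio without replacement (63"). The matching variables are age, oral contraceptive use, ethnicity, weight, adenoma type, adenoma size and number of lesions. Covariate balance is to be examined afterwards.

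Section 10.1 gives the primary analysis: "A multivariable linear regression model will be used to estimate the difference in tumour regression between the treatment group and the historical control group". It lists the terms: "The model will be adjusted for age, change in body weight, the ketogenic diet and oral contraceptive use at baseline". Section 10.2 repeats the same four as the independent variables of the primary model. Neither section says how the standard error is computed.

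Section 3 also describes a prediction model built in the same historical cohort. Its outcome is regression to below 5 cm at 1 and 2 years, and its predictors include diameter at diagnosis and adenoma subtype. Section 4.1 admits adenomas of any size.

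**The concern.** Only two of the seven matching variables, age and oral contraceptive use, reach the primary model. Diameter and subtype, which the protocol itself treats as prognostic, do not.

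Matching brings the two groups closer on the omitted variables, so these contribute less to the variation of the estimated diet effect than they would with unmatched groups. The regression does not know this. It counts all patient-to-patient spread due to those variables as residual noise, so its standard error tends to exceed the true one. Any imbalance that survives matching also stays in the estimate. The study is not randomised and this model carries its main conclusion, so the confidence interval and the handling of leftover imbalance both matter.

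**Working it through.** **1. The plan's own sample size.** Section 4.4: "With a two-sided alpha set at 0.05, power at 0.95, we calculated that at least 51 subjects are required", for 13 mm, which is 20% of 65 mm. No SD is stated. Assume it comes from the 6-month interquartile range of 56 to 80 mm: SD = (80 − 56)/1.349 = 17.8 mm. Unpaired, n per group = 2 × [17.8 × (1.960 + 1.645)/13]² ≈ 49. With SD 18 it is 50, or 51 with the t distribution. So 51 is reproduced as an unpaired per-group number. A one-sample or paired reading with the baseline range, SD = (100 − 65)/1.349 = 25.9, gives 52 and cannot be excluded. Neither SD is that of the endpoint, change in diameter.

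**2. Where the excess comes from.** Let σ be the residual SD once all matching variables are in the model, and τ the SD contributed by the omitted ones. With 51 pairs:
- stated model: SE ≈ √[2(σ² + τ²)/51]
- model with the matching variables: SE ≈ √(2σ²/51)

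With σ = 12 mm (assumed), the second is √(2 × 144/51) = 2.38 mm. The stated model's true variability lies between the two values, depending on how well matching balances the omitted variables.

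**3. Simulation in mm.** Common assumptions: 51 diet patients matched 1:1 to 180 controls by optimal propensity-score matching, residual SD 12 mm, weight change left out of the model.

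| Extra regression per mm of baseline diameter | SE reported by stated model | Actual SD of estimate | Ratio | Type I error |
|---|---|---|---|---|
| 0 | correct | – | about 1 | – |
| 0.25 mm | 2.64 | 2.49 | 1.06 | 3.9% |
| 0.5 mm | 3.27 | 2.63 | 1.24 | 1.0% |
| 0.5 mm (separate run) | 3.31 | about 2.7 | about 1.23 | near 1% |

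In the last row, adding the matching variables cut the SE to 2.39 mm, in line with 2.38 from step 2. The half-width of the 95% interval falls from 1.985 × 3.31 = 6.6 mm to 1.985 × 2.39 = 4.7 mm. Clustering on the pair without adding covariates moved the SE only from 3.31 to 3.13.

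**4. Simulation in SD units.** One unit is 17.8 mm; 1,500 runs per setting. Type I error is taken about the mean of the estimates, so it excludes bias from leftover imbalance.

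| Outcome variance explained by omitted variables | Reported SE | Actual SD | Ratio | Type I error |
|---|---|---|---|---|
| 0% | 0.198 | 0.200 | 0.99 | 5.5% |
| 30% | 0.198 | 0.176 | 1.12 | 2.1% |
| 50% | 0.197 | 0.161 | 1.23 | 1.7% |
| 70% (extreme) | 0.196 | 0.138 | 1.42 | 0.5% |
| 50%, strong size-by-diet interaction | 0.194 | 0.208 | 0.93 | 5.9% |
| 10%, strong size-by-diet interaction | 0.209 | 0.225 | 0.93 | 7.0% |

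In the 50% row the within-pair residual correlation was about 0.04. Clustering alone gave 0.191, and adding the matching variables gave 0.141 (0.197 × 17.8 = 3.5 mm against 0.141 × 17.8 = 2.5 mm).

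**5. Power.** Power ≈ Φ[(effect − 1.985 × reported SE)/actual SD]. At the planned 13 mm:
- slope 0.25: (13 − 5.24)/2.49 = 3.12, or 99.9%
- slope 0.5: (13 − 6.49)/2.63 = 2.48, or 99.3%

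For a true effect of 8 mm, simulated power was 88% and 71% with the stated covariates less weight change. It was 92% in both cases with the matching variables added and pair-clustered errors.

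**6. Leftover imbalance.** With those slopes, each 1 mm of remaining difference in mean baseline diameter moves the estimated diet effect by 0.25 to 0.5 mm.

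**The case against.** A reader might infer that section 10.1 treats matched pairs as independent patients and that its standard error and p-value are therefore wrong. The protocol does not support that. It names no variance estimator, and pair-clustered errors may be specified in a statistical analysis plan that is not at hand. The unpaired sample size, and section 10.2's explicit handling of repeated measurements elsewhere, hint at an unpaired analysis but do not establish it. Nor is pairing the main driver: clustering alone changes little, and in a further run plain and clustered errors were 2.39 and 2.41 mm once the covariates were entered.

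Three further objections stand in part.
- The direction is conditional. The error vanishes if the omitted variables are not prognostic, and reverses slightly under a strong size-by-diet interaction.
- The simulations leave out change in body weight, which section 10.1 includes. With an assumed 6 kg difference between groups (SD 5 kg), the stated model's SE rose to 3.15 and 3.97 mm for the two slopes, and power at 13 mm was 98.9% and 90.9%.
- The 8 mm effect is not the planned one, and a conservative test does not undermine a positive result.

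The omission of covariates is untouched by this. Section 10.1 gives an explicit covariate list, so it is not a detail left open for a later document. Checking balance after matching does not correct what imbalance remains.

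**Conclusion.** The concern holds in a conditional form. The primary model omits five of the seven matching variables, among them two that the protocol itself names as predictors of regression. That prediction model concerns regression to below 5 cm, so an effect on change in diameter is probable, not proven. Given such an effect and a roughly homogeneous diet effect, the reported standard error is probably too large, by about 0 to 25% (more only in the extreme 70% setting). The test is then conservative, precision is lost, and residual imbalance is left in the estimate.

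It would go too far to say that the stated p-value is certainly wrong, or that the trial lacks power for its planned effect. Power at 13 mm is largely kept under the simulated assumptions; the cost falls on smaller true effects. All figures rest on an assumed residual SD and assumed prognostic strength, since the protocol gives no SD for change in diameter.

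**What to change.** In section 10.1, add the baseline matching variables to the primary model fitted on the matched set: at least baseline diameter and adenoma type, preferably also number of lesions and baseline weight. Pair-clustered standard errors are an optional safeguard that changes little once these covariates are in. Main-effect adjustment does not cure the interaction case: with the 50% interaction setting the adjusted SE was 0.183 against an actual 0.202. Clustering the stated model there moved its SE part of the way, from 0.194 to 0.199 against 0.208.

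In the subpopulation of about 20, add baseline diameter first and the others only as its size allows. Whether change in body weight belongs in the model is a separate question that this change does not settle.

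The cost is a sentence of text and a few degrees of freedom. The variables are already needed for matching, so no new data or patients are required.

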WMO	Medical Research Involving Human Subjects Act; in Dutch: Wet Medisch-wetenschappelijk Onderzoek met Mensen

SUMMARY

Rationale: Hepatocellular adenoma (HCA) is an uncommon, solid and benign liver lesion. Typically, it is a solitary lesion found in women within their reproductive years and it is strongly associated with the use of oral contraceptive medication (OC). Development of HCA is also associated with obesity and metabolic syndrome. More recently, studies have shown a rising incidence of HCA diagnosis, current prevalence is estimated to be between 0.001 and 0.004%. HCA consists of several subtypes: inflammatory, steatotic, β -catenin mutation associated and unspecified. A higher BMI is associated with inflammatory HCA, which is also associated with multiple lesions. Steatotic HCA more often consist of single lesions.

Management of HCA requires a multidisciplinary approach. For female patients, it depends on the associated symptoms, lesion size and location. All female patients are advised to stop using OC and maintain a healthy body weight. Women with HCA can be included in a surveillance period ("Wait-and-see"-strategy) for 6 months, after which a contrast-enhanced magnetic resonance imaging (MRI) is performed. The aim is to predict if larger lesions (>5cm) will regress, thus avoiding unnecessary surgery. Treatment modalities to further enhance the regression and avoid surgery are an interesting research possibility. As overweight is frequently observed in women with liver adenoma, metabolic changes are assumed to play a role and diet may help to reduce tumour size.

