2. OBJECTIVES

Primary Objective: to determine the effect of a moderate calorie restricted, ketogenic diet on the reduction in size of hepatocellular adenoma after 6 months in adult female patients.

Secondary Objectives:

- To determine the feasibility / adherence to the ketogenic diet
- To identify predictors of the primary endpoint
- To assess possible change in the estimated chance of HCA regression to 0,5 cm at 1-2 years due to the ketogenic diet, estimated by prediction model.
- To determine the change in liver fat content
- To investigate potential side effects & burden of diet
- To determine the effect on Quality of Life (QoL)
- To assess change in body weight and plasma parameters
- To investigate the effect of the diet on change in body composition and resting energy expenditure

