5. TREATMENT OF SUBJECTS

5.1 Investigational product/treatment

All subjects will receive a diet for 6 months (see table 1 & 2 for the example diet). In this ketogenic diet the amount of carbohydrates is restricted, the first three months to approximately 35 grams per day, the second part for month 4-6 to approximately 60 grams per day. This amount of carbohydrates will lead to ketogenesis. Emphasis is placed on the use of products high in polyunsaturated and monounsaturated fatty acids (diet margarines, oils, fish, nuts), preferably with vegetable and marine sources of protein, in concordance with the national nutritional guidelines (64). We aim to moderately reduce the calories to about 70-80% of the daily energy requirements.

After the study period of 6 months, participants are free to choose which diet they want to follow. They can choose to keep following the moderate carbohydrate restricted diet, or switch to a diet according to the national nutrition guidelines. If they would like advice from a dietician, they can be referred to a dietician via their family doctor.

After participating in this study, subjects will receive further treatment according to standard clinical practice: they will be included in regular follow-up or undergo treatment for their HCA. The frequency of follow-up or possible invasive treatment depends on the findings on the MRI made after six months and the calculated chance of regression, according to current protocol.

Diet Overview:

Month 1-3: Low carbohydrate, ketogenic diet containing approximately 1500 kcal, 35 grams of carbohydrate and 0.8 g/kg of protein /day

Month 4-6: Moderate carbohydrate, ketogenic diet containing approximately 1500 kcal, 60 grams of carbohydrate and 0.8 g/kg of protein /day

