10.2 Secondary study parameters

In the secondary analysis, the multivariable linear regression model analysis from the primary analysis will be used to identify independent variables (age, change in body weight, subjected to ketogenic diet and oral contraceptive use at baseline) as predictors of the primary endpoint. An additional analysis will be performed including adherence to the diet as independent variable.

Analysis for adherence to the ketogenic diet will be done via descriptive statistics. Adherence to the diet will be calculated as a percentage.

Side effects of the ketogenic diet will be analyzed via descriptive statistics. Occurrence of side effects will be given as a percentage.

Results of the prediction model/chance assessment tool (30), providing the estimated chance (%) of HCA regression to 0,5 cm at 1 and 2 years after diagnosis will be compared between our intervention group and the matched historical controls by the Chi-square test.

Change in liver fat content (%) will be compared in our intervention group by a multivariable linear regression model. The independent variables in this model will include age, change in body weight and oral contraceptive use at baseline. An additional analysis will be performed including adherence to the diet as independent variable.

Changes in plasma parameters will be compared in our intervention group by using descriptive statistics, t-test in the case of continuous outcome variables with normal distribution or non-parametric test in the case of non-normality. The Chi-square test will be used for categorical data.

Change in quality of life will be compared over time in our intervention group by a mixed-effects model analysis, taking repeated measurements into account. The independent variables in this model will include age and change in body weight. An additional analysis will be performed including adherence to the diet as independent variable.

Mean change in body weight, change in body composition and resting energy expenditure will be estimated in our intervention group by a mixed-effects model analysis, taking repeated measurements into account. The independent variables in this model will include age and sex. An additional analysis will be performed including adherence to the diet as independent variable.

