11.4 Benefits and risks assessment, group relatedness

Based on the hypothesis and earlier studies that long-term caloric restriction and the ketogenic diet induce beneficial effects, the diet intervention group may experience better subjective wellbeing and weight loss compared to those in the control group. Potential side-effects can be managed by the dietician involved. This study aims to investigate the merits of caloric restriction and the ketogenic diet in the treatment of hepatocellular adenoma.

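### The primary model adjusts for weight change, which the diet is expected to cause, so the diet coefficient is not the total effect named in the objective

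*Protocol*

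**What the plan says.** The primary objective (Protocol section 2) is "to determine the effect of a moderate calorie restricted, ketogenic diet on the reduction in size of hepatocellular adenoma after 6 months". Calorie restriction is thus part of the treatment under study.

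For the analysis, section 10.1 says: "A multivariable linear regression model will be used to estimate the difference in tumour regression between the treatment group and the historical control group". The covariates follow: "The model will be adjusted for age, change in body weight, the ketogenic diet and oral contraceptive use at baseline". The subpopulation gets the same model without oral contraceptive use. Neither population has a stated regression model without weight change.

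Elsewhere the protocol treats weight change as something the diet brings about:
- Section 5.1: "We aim to moderately reduce the calories to about 70-80% of the daily energy requirements".
- Section 11.4: "the diet intervention group may experience better subjective wellbeing and weight loss compared to those in the control group".
- Section 8.1.2 lists change in body weight among the secondary endpoints.
- The Summary starts from the frequency of overweight in these women and continues: "metabolic changes are assumed to play a role and diet may help to reduce tumour size".

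Section 4.4 sizes the study on an additional decrease of 13 mm with the diet, two-sided alpha 0.05, power 0.95 and at least 51 subjects. Section 3 specifies 1:1 propensity-score matching, with weight among the matching variables.

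**The concern.** A covariate in a treatment comparison should not be something that the treatment changes. With weight change in the model, the diet coefficient compares a woman on the diet with a historical control who had the same weight change. Any shrinkage that the diet achieves by making women lose weight is credited to the weight term. What is left is at best an effect not passing through weight, which no objective asks for.

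The comparison is also not randomised. Weight change may share causes with tumour regression, such as general motivation or metabolic state, and conditioning on it then brings those causes into the diet coefficient. Even as a weight-independent effect, the coefficient would need assumptions that the protocol does not state.

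At stake is the meaning of the only primary regression estimate, and the power claimed for it.

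**Working it through.** **1. The plan's own figure.** Section 4.4 gives a follow-up diameter of median 65 mm (IQR 56-80). The effect is 20% of 65 = 13 mm. No SD is stated. Assuming normality, SD = (80 - 56)/1.349 = 17.8 mm. Per group, n = 2 × (1.960 + 1.645)² × (17.8/13)² = 48.7, so 49; the t-test version gives 50. The stated 51 is therefore reproduced to within two, read as 51 diet subjects plus 51 matched controls. At 51 per group, t-test power is about 95% with SD 17.8 or 18 mm. The sample size thus rests on the full 13 mm in a comparison without weight change.

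**2. Assumptions for the illustration, none given in the documents.** SD 18 mm within group (rounded from step 1; it describes follow-up diameter, because the SD of the reduction itself is not given). Diet-control difference in weight change D = 5 or 8 kg. Within-group SD of weight change 5 kg. Share m of the 13 mm acting through weight: 0 to 75%.

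**3. Formulas.**
- Diet coefficient with weight change in the model = 13 × (1 - m).
- Slope on weight change b = 13m/D; residual SD = √(18² - (5b)²).
- Variance inflation VIF = 1 + 0.25D²/5², which is 1.25 at 5 kg and 1.64 at 8 kg.
- SE = residual SD × √(2/51) × √VIF.
- Power from the non-central t with 99 df.

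Without weight change, SE = 18 × √(2/51) = 3.56 mm.

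| Share through weight | Coefficient (mm) | SE at 5 kg / 8 kg (mm) | Power at 8 kg to 5 kg |
|---|---|---|---|
| 0% | 13 | 3.99 / 4.56 | 81-90% |
| 25% | 9.75 | 3.92 / 4.54 | 57-69% |
| 50% | 6.5 | 3.72 / 4.45 | 30-41% |
| 75% | 3.25 | 3.35 / 4.30 | 12-16% |

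**4. Simulation check.** With D = 6 kg, SD 17.8 mm, 51 per group and 3,000 runs, the adjusted coefficient averaged 12.9, 9.8, 6.4 and 3.2 mm at shares of 0, 25, 50 and 75%, with power 87, 67, 37 and 14%. Without weight change it averaged about 13 mm throughout, with power 95-96%.

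**5. Common causes.** Add an unmeasured factor with loading 0.5 on both weight loss and regression, half of the effect mediated, D = 6 kg. The adjusted coefficient averaged about 1.5 mm in simulation, not 6.5 mm. Arithmetic agrees: residual SD = √(17.8² - (5 × 13 × 0.5/6)²) = 17.0 mm, shift = 6 × 17.0 × 0.25/5 = 5.1 mm, and 6.5 - 5.1 = 1.4 mm. If the loadings have opposite signs, the shift goes the other way. With no mediation it is 6 × 17.8 × 0.25/5 = 5.3 mm, giving 13 + 5.3 = 18.3 mm, which is above the true 13 mm.

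**The case against.** The best defence is that the investigators want the ketogenic effect beyond weight loss. Usual care already advises a healthy weight (sections 1 and 4.1), and section 1 cites ketone-body and IGF-1 mechanisms and a eucaloric ketogenic study. That question is legitimate, but section 2 does not ask it, section 4.4 is not powered for it, and the intention-to-treat statement in section 10 fits the total effect better. Step 5 shows that the adjustment would not isolate it reliably either.

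Section 8.1.1 describes comparing mean regression with the earlier cohort, which reads like a comparison without covariates, and section 10.2 uses the same model to report weight change as a predictor. A reader might infer that a diet working through weight loss would simply be reported as ineffective. The documents do not support that: the weight-change coefficient could show such a benefit. But section 8.1.1 does not displace the model in section 10.1.

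Other stronger readings also fail:
- *Baseline weight is an unhandled confounder.* It is a matching variable with planned balance checks (section 3).
- *The bias is certainly toward no effect.* Step 5 shows otherwise.
- *The standard error is always inflated.* At 75% and 5 kg it is 3.35 mm against 3.56 mm unadjusted, because the gain in residual variance outweighs the VIF.
- *The single-arm models in section 10.2 refer to a woman with no weight loss.* The liver-fat model states: "The independent variables in this model will include age, change in body weight and oral contraceptive use at baseline". A linear model evaluated at mean covariates still returns the mean change, and centring can be left to a statistical analysis plan.
- *The adherence model cannot be fitted because controls have no adherence value.* The text is "An additional analysis will be performed including adherence to the diet as independent variable", which does not say that controls are included.

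**Conclusion.** The point holds for the primary model in section 10.1 and its subpopulation counterpart. By the protocol's own account, weight change is an expected result of the intervention, so the diet coefficient is not the total effect in the objective and in the sample size. This follows from the covariate list and needs no numerical assumption, although the numerical gap closes if none of the effect runs through weight and there are no common causes.

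How large the gap is cannot be read from the protocol, which gives neither the share acting through weight nor the expected weight difference. The table is a range under assumptions, not a forecast. Its mildest row leaves the coefficient at 13 mm but lowers power to 81-90%; at a 50% share the coefficient is halved and power is 30-41%.

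**What to change.** In section 10.1, delete the weight-change term from the primary model and adjust only for variables measured at baseline. Baseline weight may be included; it is already collected (section 8.1.3) and already used for matching. Make the same deletion in the subpopulation model. Keep a model with weight change only as an exploratory mediation analysis, labelled as such, with its assumption about common causes stated.

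If a weight-independent effect is what is wanted, it should be declared as a separate objective, and the sample size in section 4.4 should not be presented as covering it.

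The cost is a change of wording: no new data, visits or patients.
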